End-of-Treatment: This visit should be performed on trial day 169 (+2 days) (ie, 7 days [+2 days] after the last dosing visit) for all participants who have completed the 24-week treatment period, whether they were still receiving IMP or not. Every effort should be made to schedule every visit on the exact day (which is relative to baseline randomization [visit 1]).

Early Discontinuation: This visit should be performed on the day of early discontinuation for all participants that discontinue the trial early.

Follow-up Period: For participants discontinuing the trial early (with the exception of participants who withdraw their consent) or who do not roll over to the open-label extension trial. The follow-up period will consist of 2 visits q4w (ie, 8 weeks of follow-up).

^b No trial-related assessment must be carried out before signing the informed consent form (ICF).

^c For further confirmation of eligibility at visit 1, the assessment of inclusion and exclusion criteria should be performed prior the start of any trial-related procedure and randomization.

^d Platelet count is measured locally and can be performed within 1 day (for postbaseline visits) of the next procedure as per schedule of activities (both dosing and nondosing visits). Eligible participants should have a mean platelet count of <30x10⁹/L from at least 3 documented, qualifying counts within the 3 preceding months where at least 2 of the qualifying counts must be taken during the screening period: 1 platelet count collected during the screening period

and the predose platelet count on the day of randomization (visit 1). If the third count is not available from the 3 preceding months, this third platelet count can be obtained during the screening period. [REDACTED]

^e If available at baseline.

^f Height will only be measured at the screening visit.

^g If IMP is administered, the ECG will be performed after the IMP administration.

^h Laboratory assessments include all parameters mentioned in Section 10.2. On days that IMP is administered, samples for laboratory assessments should be collected before dosing, unless otherwise requested.

ⁱ At the screening visit, if the investigator detects 1 or more screening laboratory abnormalities which are not aligned with the medical history and clinical evaluation of the participant, the result(s) should be confirmed if still within the screening window. For rescreening criteria see Section 5.4.

^j Only for women of childbearing potential.

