
 • To evaluate the use of rescue treatment and changes in concurrent ITP therapy while receiving treatment with efgartigimod PH20 SC compared to placebo PH20 SC 	
 • Rate of receipt of rescue therapy (rescue per patient per month) in the overall population • Proportion of patients for whom dose and/or frequency of concurrent ITP therapies have increased at week 12 or later in the overall population

 • To evaluate the effects of efgartigimod PH20 SC treatment on QoL measures and PRO compared to placebo PH20 SC 	
 • Change from baseline in PRO (Functional Assessment of Chronic Illness Therapy Fatigue Scale [FACIT-Fatigue], Functional Assessment of Cancer Therapy questionnaire-Th6 [Fact-Th6]) and QoL (Short Form-36 [SF-36]) at planned visits in the overall population

 • To assess the immunogenicity of efgartigimod and rHuPH20 	
 • Incidence and prevalence of antibodies to efgartigimod and/or rHuPH20 in the overall population • Titers of antibodies to efgartigimod and/or rHuPH20 in the overall population • Presence of neutralizing antibodies (NAb) against efgartigimod and/or rHuPH20, and titers of NAb against rHuPH20 in the overall population

 • To assess the PK of efgartigimod PH20 SC 	
 • Serum efgartigimod concentration observed predose (C_{trough}) in the overall population

To assess the PD effects of efgartigimod PH20 SC	
Pharmacodynamics markers: total IgG and antiplatelet antibody levels in the overall population
Exploratory	

[REDACTED]	
[REDACTED]

[REDACTED]	
[REDACTED]

[REDACTED]	
[REDACTED]

[REDACTED]	
[REDACTED]

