6.5. Screening and Treatment

After the informed consent has been obtained, the participant will be screened (screening period of maximum 14 days) at the investigative site for eligibility based on the inclusion and exclusion criteria defined in Section 5.1 and Section 5.2, respectively.

The assessments as specified in the SoA, Section 1.3 will be performed during screening.

All participants will initially receive qw SC injections from visit 1 to 4 (consecutive administrations of IMP should be at least 5 days apart).

Based on the platelet counts as of visit 2, the dosing frequency can be altered from visits 5 to 16 (consecutive administrations of IMP should be at least 5 or 12 days apart for the qw or q2w administration schedule, respectively) according to the following rules (the change in dosing frequency will occur at the current visit):

- Reduce from qw to q2w in participants having platelet counts of $\geq 100 \times 10^9/L$ for 3 out of 4 consecutive visits (the fourth visit being the current visit), and having a platelet count of $\geq 100 \times 10^9/L$ at the last of these 4 visits
 - OR –
 - Reduce from qw to q2w in participants having platelet counts of $\geq 100 \times 10^9/L$ for 3 consecutive visits
 - Note: In this case, no IMP will be administered at the last visit confirming the qualifying platelet counts of $\geq 100 \times 10^9/L$.
- Increase from q2w to qw in participants whose platelet counts drop to $< 100 \times 10^9/L$ on 2 consecutive visits
 - OR –
 - $< 30 \times 10^9/L$ at 1 visit
 - OR –

in participants who receive rescue therapy (see Section 6.6.4)

- Postbaseline platelet count can be performed within 1 day of the next procedure as per SoA (both dosing and nondosing visit), allowing the results to be incorporated into the criteria above.

From visits 17 to 24, the dosing frequency is fixed for each individual participant (ie, either qw or q2w regimen), based on the regimen the participant was receiving at visit 16 or at the last visit at which IMP was administered.

Exceptions to the fixed dosing frequency are:

- Continued qw dosing for participants requiring rescue therapy
- Continued q2w dosing for participants resuming IMP when the platelet count falls to $<150 \times 10^9/L$ after having had platelet counts $>400 \times 10^9/L$

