6.8. Intervention After the End of the Trial

After a participant has completed the trial, has withdrawn/discontinued early, or has completed the 2 follow-up visits, usual treatment will be administered if required, in accordance with the trial site's standard of care and generally accepted medical practice depending on the participant's individual needs.

Eligible participants who have completed the 24-week randomized trial period can enter the open-label extension trial ARGX-113-2005 to receive efgartigimod (see Section 4.1).

- Participants who are receiving a qw regimen:
 - The baseline visit (including the first dose of IMP) of ARGX-113-2005 will occur on the same day as the end-of-treatment visit of ARGX-113-2004. Assessments that were performed at the end-of-treatment visit of ARGX-113-2004 should not be repeated at visit 1 (baseline) of ARGX-113-2005.
- Participants who are receiving a q2w regimen:
 - If visit 24 of ARGX-113-2004 is a dosing visit, then the baseline visit of ARGX-113-2005 (including the first dose of IMP) will occur 7 days after the end-of-treatment visit of ARGX-113-2004.
 - If visit 24 of ARGX-113-2004 is a nondosing visit, then the baseline visit (including the first dose of IMP) of ARGX-113-2005 will occur on the same day as the end-of-treatment visit of ARGX-113-2004. Assessments that were

performed at the end-of-treatment visit of ARGX-113-2004 should not be repeated at visit 1 (baseline) of ARGX-113-2005.

- Participants who are receiving a qw regimen who meet the criteria (Section 6.5) to switch to a q2w regimen based on their platelet counts at the ARGX-113-2004 end-of-treatment visit:
 - The baseline visit of ARGX-113-2005 (including the first dose of IMP) will occur 7 days after the ARGX-113-2004 end-of-treatment visit.

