4.2.3 Presentation of results

For tables by fixed dosing regimen, only visits of the fixed dosing schedule period (ie, baseline up to week 3 and week 16 up to week 24) will be tabulated. In this first period of baseline up to week 3, all participants have weekly dosing per protocol. For the second period, the fixed dosing regimen is defined as explained in section 3.6.2.

Individual concentration data and actual blood sampling times from start of injection for PK assessments will be listed. Data issues like time deviations will be mentioned in the remarks.

Descriptive statistics on concentration data will be presented in tables per visit (and fixed dosing regimen (weekly or every other week)). A similar table will be created by ADA and NAb against efgartigimod, and antibodies against rHuPH20 Participant Classification.

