14.2.7.1 Intercurrent Events Occurrence in Participants with Chronic ITP FAS-chronic

PHARMACOKINETICS

14.2.8.1.1 Descriptive Statistics of Efgartigimod Trough Concentrations (unit) by Visit (and Fixed Dosing Regimen) and Time Point PK

PHARMACODYNAMICS

14.2.9.1 Descriptive Statistics of Actual Values and Changes from Baseline in Total IgG Level (g/L) by Fixed Dosing Regimen and Overall and by Visit PD

14.2.9.2.1 Descriptive Statistics of Actual Values and Changes from Baseline in Total IgG (g/L) by Fixed Dosing Regimen and Overall and by Visit by History of Splenectomy PD

14.2.9.2.2 Descriptive Statistics of Actual Values and Changes from Baseline in Total IgG (g/L) by Fixed Dosing Regimen and Overall and by Visit by Receiving Concurrent ITP Therapies at Baseline PD

14.2.9.2.3 Descriptive Statistics of Actual Values and Changes from Baseline in Total IgG (g/L) by Fixed Dosing Regimen and Overall and by Visit by Baseline Platelet Count PD

14.2.9.2.4 Descriptive Statistics of Actual Values and Changes from Baseline in Total IgG (g/L) by Fixed Dosing Regimen and Overall and by Visit by Number of Prior ITP Therapies PD

14.2.9.2.5 Descriptive Statistics of Actual Values and Changes from Baseline in Total IgG (g/L) by Fixed Dosing Regimen and Overall and by Visit by Time Since Diagnosis PD

14.2.9.2.6 Descriptive Statistics of Actual Values and Changes from Baseline in Total IgG (g/L) by Fixed Dosing Regimen and Overall and by Visit by Sex at Birth PD

14.2.9.2.7 Descriptive Statistics of Actual Values and Changes from Baseline in Total IgG (g/L) by Fixed Dosing Regimen and Overall and by Visit by Region PD

14.2.9.2.8 Descriptive Statistics of Actual Values and Changes from Baseline in Total IgG (g/L) by Fixed Dosing Regimen and Overall and by Visit by Age Category PD

14.2.9.2.9 Descriptive Statistics of Actual Values and Changes from Baseline in Total IgG (g/L) by Fixed Dosing Regimen and Overall and by Visit by Race PD

	Statistical Analysis Plan	
ARGX-113-2004	Final analysis	Final 1.0 of 7NOV2023

- 14.2.9.2.10 Descriptive Statistics of Actual Values and Changes from Baseline in Total IgG (g/L) by Fixed Dosing Regimen and Overall and by Visit by Ethnicity Category PD
- 14.2.9.2.11 Descriptive Statistics of Actual Values and Changes from Baseline in Total IgG (g/L) by Fixed Dosing Regimen and Overall and by Visit by Weight Category at Baseline PD
- 14.2.9.3.1 Frequency Tabulation for Antiplatelet Antibody Categories at Baseline PD

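### At Week 24 the every-other-week PK and IgG rows can mix 7-day and 14-day post-dose samples, and SAP 4.2.1 does not say how its exclusion applies there

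*SAP*

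**What the plan says.** **Endpoint.** Protocol 3 names one PK secondary endpoint: "Serum efgartigimod concentration observed predose", that is, C_trough.

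**End-of-Treatment visit.** Protocol 1.3 fixes one day for everyone who completes: "This visit should be performed on trial day 169 (+2 days) (ie, 7 days [+2 days] after the last dosing visit". PK and PD samples are scheduled at it. Footnote n asks for PK and PD samples to be predose on a dosing day. Footnote p cancels the visit 24 sample if no dose is given then. The End-of-Treatment column carries no footnote p.

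**Dosing around that visit.** Protocol 6.5 sets the spacing: "consecutive administrations of IMP should be at least 5 or 12 days apart for the qw or q2w administration schedule, respectively". Protocol 6.8 recognises two q2w groups.
- "If visit 24 of ARGX-113-2004 is a dosing visit, then the baseline visit of ARGX-113-2005" is put off by a week, so these participants receive nothing on day 169.
- "If visit 24 of ARGX-113-2004 is a nondosing visit", the first extension dose is given on the End-of-Treatment day itself.

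**Analysis.**
- SAP Table 5 defines the PK and total IgG windows by study day only.
- SAP 4.2.1 expects every PK sample to be predose on a dosing day and removes concentrations outside the permitted ranges from the by-timepoint statistics. It states no numerical range.
- SAP 4.2.3 and 4.3.3 tabulate by visit and fixed regimen: "only visits of the fixed dosing schedule period (ie, baseline up to week 3 and week 16 up to week 24) will be tabulated".
- Table 14.2.8.1.1 in SAP 8.1 is titled "Descriptive Statistics of Efgartigimod Trough Concentrations (unit) by Visit (and Fixed Dosing Regimen) and Time Point".
- For total IgG, 4.3.3 excludes results after treatment discontinuation. It has no rule on time since dose.

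**The concern.** A trough summary is interpretable only if the samples in a row share the same time since the last dose. At Week 24 the q2w row can hold two kinds of sample: some halfway through the dosing interval, others at its end. Week 24 is the last on-treatment time point at which exposure and IgG are shown by regimen, and C_trough is a named secondary endpoint. Mid-interval concentrations in a row labelled trough would make q2w exposure look higher than it is. They could also produce a change from Week 23 to Week 24 that reflects only sampling time.

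The wording of 4.2.1 adds a second problem. Two programmers could read it differently and produce different Week 24 PK tables.

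**Working it through.** **1. Reproduce the plan's own figure.** Weekly visits in Protocol 1.3 give day(v) = 1 + 7(v − 1).
- Visit 23: 1 + 7 × 22 = 155.
- Visit 24: 1 + 7 × 23 = 162.
- End-of-Treatment: 169.
- 169 − 162 = 7 days, as the protocol states.

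**2. Time since last dose at End-of-Treatment.**

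| Group | Last dose | Nominal | With +2-day windows |
|---|---|---|---|
| Weekly (qw) | day 162 | 7 days | 169 − 164 = 5 to 171 − 162 = 9 |
| q2w, dosed at visit 24 | day 162 | 7 days | 5 to 9 |
| q2w, last dosed at visit 23 | day 155 | 169 − 155 = 14 days | 169 − 157 = 12 to 171 − 155 = 16 |

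The two q2w ranges do not overlap. Protocol 6.8 agrees: the first q2w group has its next dose 7 days after End-of-Treatment, the second on the day itself.

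**3. Analysis windows.** In SAP Table 5, Week 23 covers days 156 to 165 and Week 24 runs from day 166 to the end of the treatment phase. Both q2w groups therefore fall in Week 24. The scheduled visit 24 sample does not have this mix: under footnote p it exists only if a dose is given, so for q2w it is nominally a 14-day predose sample.

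**4. Does another rule separate the groups?**
- *Total IgG:* no. The discontinuation exclusion does not touch completers.
- *PK, 4.2.1 not applied to a scheduled visit:* both groups enter the q2w trough row.
- *PK, 4.2.1 applied literally (dosing day only):* the mid-interval q2w samples are removed. So are 7-day qw and 14-day q2w troughs in participants who do not roll over, and all follow-up PK samples, although Table 5 defines follow-up windows for PK.
- *Missed-dose exclusion in 4.2.1:* not relevant. Protocol 6.4.1 counts a dose as missed only when the visit is missed.

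**5. Illustration of size for concentration.** The documents give neither a half-life nor the share of q2w participants dosed at visit 24. Assume mono-exponential decline with half-life h and a share f dosed at visit 24. Then r = C(day 7)/C(day 14) = 2^(7/h), and the pooled mean relative to the 14-day trough is 1 + f(r − 1).

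| h (days) | r | f = 0.25 | f = 0.50 | f = 0.75 |
|---|---|---|---|---|
| 3 | 5.04 | 2.01 | 3.02 | 4.03 |
| 5 | 2.64 | 1.41 | 1.82 | 2.23 |
| 7 | 2.00 | 1.25 | 1.50 | 1.75 |

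The direction is upward for any half-life. The size depends wholly on the two assumptions. No similar calculation is possible for IgG.

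**The case against.** The strongest reply is that 4.2.1 already deals with PK. A q2w participant dosed at visit 24 has no dose on day 169, so a rule that keeps only predose samples from dosing days removes exactly the mid-interval values. Footnote n and Protocol 8.7 put the same sampling condition on the PD samples. This stands to the extent that pooling in the PK trough table cannot be asserted as fact. It does not close the point. The End-of-Treatment sample is scheduled, so it is not plainly a deviation, and the literal reading discards valid troughs.

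Second, total IgG is never labelled a trough. It is summarised as observed at each visit, and those descriptions are accurate. This stands. A reader might infer that the Week 24 IgG summaries are wrong, or that they overstate suppression on q2w. The documents do not support that, because they give no IgG difference between day 7 and day 14.

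Third, the reach is small. These are descriptive q2w rows at one visit, with their subgroup and antibody-classification repeats. No stated PK or PD objective compares qw with q2w, and actual PK sampling times from injection are listed. This stands too, and it limits the severity.

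**Conclusion.** The point holds as a minor one. At Week 24 the q2w rows can combine samples taken 7 and 14 days after the last dose, and the SAP does not separate them. Where both groups are present, pooling is certain for total IgG. For PK, the SAP as written leads either to a mixed row under a trough title or to the loss of valid troughs, depending on how 4.2.1 is read.

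Mixing moves the q2w mean concentration upward relative to a true 14-day trough. The figure of about 1.5 to 3.0 times is an illustration only: it assumes a half-life of 3 to 7 days, mono-exponential decline and an even split, none of which is in the documents. It should not be read as an estimate of bias in this trial. Neither size nor direction is established for IgG. The overlap of Week 24 with the response window might suggest an effect on efficacy, but no efficacy endpoint or alpha-controlled test uses these tables.

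**What to change.** **SAP 4.2.1.** State that End-of-Treatment PK samples are not excluded merely because no IMP is given that day.

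**SAP 4.2.3 and 4.3.3.** Split the Week 24 q2w rows for PK and total IgG by whether visit 24 was a dosing visit. Label only the nondosing group (last dose at visit 23) as trough, and label the dosing group mid-interval. Leave the qw rows as planned.

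**Special cases.** SAP 3.6.2 sets the fixed regimen from analysis week 16 (or from rescue therapy shortly before visit 16), while Protocol 6.5 and 6.6.4 allow a later move to qw after rescue. Classify such participants by their actual regimen at visit 24; a split on days since dose alone would call their 7-day qw troughs mid-interval. Doses withheld under Protocol 6.7 can give other intervals. List or footnote those participants; do not drop them.

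**Cost.** A few sentences in the SAP and one derived variable from dosing records already collected. The q2w Week 24 trough row will have a smaller n. This is a cheap improvement that needs no new data.

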4.3 PHARMACODYNAMICS

4.3.1 Available data

The following PD parameters will be measured:

- Total Immunoglobulin G (IgG)
- antiplatelet antibody levels targeting GPIIb/IIIa, GPIb/IX, GPV and GPIa/IIa.

For the statistical analysis, only the results obtained with the immunoturbidimetry in vitro diagnostic (IVD) assay will be used.

4.3.2 Derivation rules

Antiplatelet antibody positivity at a certain time point is defined as having at least one out of four values of the individually tested glycoproteins above the pre-defined optical density (OD) cutoff at that time point (positive if > 0.129). If at a timepoint one or more individually tested glycoprotein is missing and none is positive, the antiplatelet antibody will be shown as unevaluable.

Antiplatelet antibody positivity for a particular glycoprotein at a certain time point is defined as having an OD value above the pre-defined OD cutoff for that particular glycoprotein at that time point (positive if > 0.129).

For antiplatelet antibodies, a best-case analysis visit will be derived if at least one non-missing postbaseline result is available. The outcome at this visit is negative if at least one postbaseline visit has a negative result. If the outcome is unevaluable at all postbaseline visits, best-case analysis visit result is unevaluable. Otherwise it is positive. All non-missing postbaseline values during the treatment phase, including unscheduled assessments will be considered when deriving the best-case analysis visit.

	Statistical Analysis Plan	
ARGX-113-2004	Final analysis	Final 1.0 of 7NOV2023

4.3.3 *Presentation of results*

Total IgG results after treatment discontinuation will be excluded from the tables.

For tables by fixed dosing regimen, only visits of the fixed dosing schedule period (ie, baseline up to week 3 and week 16 up to week 24) will be tabulated. In this first period of baseline up to week 3, all participants have weekly dosing per protocol. For the second period, the fixed dosing regimen is defined as explained in section 3.6.2.

For Total IgG, summary statistics will be provided in terms of actual values and changes from baseline for each visit per fixed dosing regimen and overall. Moreover, percent changes from baseline will also be presented. The summary statistics for Total IgG will be repeated for all subgroups specified in section 4.1.4.

Antiplatelet antibody results from Chinese participants will be excluded from the tables, as these were obtained with a different assay.

Frequency of antiplatelet antibody categories will be summarized at baseline for each glycoprotein and overall. Frequency of antiplatelet antibody-positive participants will be summarized per analysis visit and for the best-case analysis visit. For antiplatelet antibody-positive participants, a frequency table of the antiplatelet antibodies will be created for each glycoprotein separately (GPIIb/IIIa, GPIb/IX, GPV, GPIa/IIa) per analysis visit and for the best-case analysis visit.

All actual and change from baseline IgG and antiplatelet antibody levels data will be listed.

4.4 IMMUNOGENICITY

4.4.1 *Available data*

ADA to efgartigimod and antibodies against rHuPH20 (rHuPH20 Ab) is measured per schedule of assessment (see 9.5.1).

Immunogenicity samples are analyzed in a 3-tiered approach:

- All samples are evaluated in the ADA screening assay and are scored ADA screening positive or negative
- If a sample scored positive in the ADA screening assay, it is further evaluated in the confirmatory assay and is scored confirmed positive (positive immuno-depletion) or confirmed negative (negative immuno-depletion)
- If a sample is scored as confirmed positive, the samples are further characterized in the ADA titration assay (to determine titer) and are also further analyzed in the NAb assay to confirm neutralizing activity (positive or negative). For NAb against efgartigimod, a screening assay is performed and results will be reported as negative or positive. For NAb against rHuPH20, the same 3-tiered approach is implemented: the screening NAb assay, followed by a Nab confirmatory assay, and a titer NAb assay, according to the above described 3-tiered approach.

Note: If a sample could not be analyzed or reported as ‘positive screen’, the ADA sample status is ADA unevaluable.

[figure not shown]
	Statistical Analysis Plan	
ARGX-113-2004	Final analysis	Final 1.0 of 7NOV2023

If available, a titer result will be reported for the ADA or rHuPH20 Ab or rHUPH20 NAb confirmed positive samples. However, a titer result is not always available. This is also applicable to rHuPH20 Ab and rHuPH20 NAb results.

- In case the ADA confirmed positive sample could not be run in the titration assay (e.g. due to insufficient sample volume/quality to perform the titer analysis), the result will be described as ‘positive immuno-depletion’ and the sample should be considered as ADA positive.
- If a sample is negative in the titration assay, it will be reported as ‘negative titer’ but it should be considered as ADA positive since it was confirmed positive in the second tier.

An overview of this 3-tiered approach and all possible ADA or rHuPH20 Ab or rHuPH20 NAb sample results that will be reported by the laboratory is given below. From these reported ADA or rHuPH20 Ab or rHuPH20 NAb sample results a final ADA or rHuPH20 Ab or rHuPH20 NAb sample status needs to be derived during the statistical analysis, as presented in the final column (‘Final ADA Outcome’):

Figure 1: ADA sample status

^a missing screen includes the following terms (reported as reason not done): NA (not analysed), NR (no result), NS (no sample), and SL (sample lost). More details can be found in the IS data transfer agreement from the specialty labs to SGS SD office.

^b 'positive titer' is reported in case it was not possible to retrieve a numerical value

	Statistical Analysis Plan	
ARGX-113-2004	Final analysis	Final 1.0 of 7NOV2023

